6.4 Suspension and withdrawal

Patients who were screened and confirmed to be eligible for the study, signed the informed consent and completed the randomization were considered as enrolled. If serious program deviation, withdrawal, or death occurs, the subject study is considered to be suspended. If the subject discontinues the study after obtaining informed consent, the data before the discontinuation will still be included in the study-related analysis.

6.4.1 Pre-Procedure

In any time during the study period, even before EUS, participants could withdraw their informed consent whenever necessary. Researchers can withdraw participants before surgery according to safety considerations in the inclusion and exclusion criteria.

6.4.2 Intraprocedure

For safety reasons, the investigator may have the subject quit during the procedure. For example, the patient is not suitable for receiving the instrument for the study or the endoscopists do not use the specified instrument for any reason. If the following serious cases occur, please withdraw during the operation:

- 1) Perforation
- 2) Bleeding
- 3) Allergy to narcotic drugs
- 4) Unable to complete EUS due to obstruction or other reasons

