Expected effect:	ENDOANGEL's intended use is to effectively improve the quality of EUS scanning for physicians, enhance the cognitive ability of endoscopists in endoscopic ultrasound images, and reduce the missed diagnosis of lesions.
Primary Endpoint:	Missed scanning rate of adjacent important anatomical structures in pancreatic endoscopic ultrasonography
Secondary Endpoints:	
 1.Pancreatic lesions detection rate; 2.Cholangiopancreatic duct lesions detection rate 3.The average number of scanning in the pancreatic standard station of endoscopic ultrasonography 4.Detection rate of lesions in different pancreatic standard stations of endoscopic ultrasonography 5.Missed scanning rate of adjacent vital anatomical structures in different pancreatic standard stations of endoscopic ultrasonography 6.Mean scanning time in different pancreatic standard stations of endoscopic ultrasonography
Trail design:	Prospective, single-center, randomized controlled trial
Participants:	Male and female subjects aged 18 years or older will require a endoscopic ultrasonography, and voluntarily provide endoscopic ultrasonography imaging data and sign an informed consent form.
Sample size:	285 samples needed to be enrolled
Study Process:	Subjects who met all inclusion criteria and did not meet all exclusion criteria were included in the study before endoscopic ultrasonography. All included subjects signed an informed consent form. Subjects will be randomized prior to the start of the examination to either an Endoangel-assisted experimental group or a control group without Endoangel assistance. The operating physician completed the endoscopic ultrasonography according to the presence or absence of AI prompt. The recorder shall record the number of adjacent important structures, the number of standard stations, the operation time and the lesion detection etc. Follow-up will be performed for one week after the end of examination. The end time of follow-up is the end time of study. And the results are sent to an independent data analysis team for review.

[figure not shown]

Security	Safety incidents shall be evaluated and reported according to the quality management measures for clinical trials of medical devices
-----------------	--

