6.5 Randomization and Blinding

6.5.1 Randomization Implementation

Randomization is conducted according to the study protocol, and the random contents are implemented in an electronic system block-randomized manner ($n = 4$; experimental group/control group = 1). Randomization prior to EUS to decide whether to use EndoAngel. The researchers randomized the random results generated by the electronic system, and the generated random results were stored in the research center. The random time (accurate to minute), random person, subject number and acronym were recorded in the corresponding positions of the electronic system.

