7.4. Expected and trial-related adverse events

Previous studies have shown that the expected adverse events are basically the same as the complications of conventional endoscopic diagnosis and treatment.

The instrument used in this experiment is a medical software which is not in contact with human body. There is no difference between the experimental operation and the routine operation. The intervention measures (such as randomized process) in the experiment may slightly increase

the incidents of diagnosis and treatment.

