7.5. Risk minimization

In this study, when there are bugs in the software, doctors can still operate under their own judgment without affecting conventional diagnostic and treatment measures, greatly reducing the risk of the test.

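### Section 6.4.2 allows mid-procedure withdrawal when the study instrument is not used, a post-randomisation exit that on the natural reading exists only in the EndoAngel arm and that the per-protocol main analysis is likely to carry into the primary comparison

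*Combined protocol and SAP*

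**What the plan says.** Section 6.4.2 opens with a permissive, safety-framed clause: "For safety reasons, the investigator may have the subject quit during the procedure". One of its examples is that "the endoscopists do not use the specified instrument for any reason". A separate list of four serious events follows (perforation, bleeding, anaesthetic allergy, EUS that cannot be completed); these can occur in either arm.

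Other sections bear on what this means:

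- Section 7.4: "The instrument used in this experiment is a medical software which is not in contact with human body".
- Synopsis, study process: the comparator is "a control group without Endoangel assistance", and the operating physician works with or without the AI prompt.
- Section 6.5.1: "Randomization prior to EUS to decide whether to use EndoAngel", with "experimental group/control group = 1".
- Section 6.5.2: subjects and evaluators are blinded. The operator is not listed.
- Section 6.4: "If serious program deviation, withdrawal, or death occurs, the subject study is considered to be suspended". Data gathered before discontinuation stay in the analysis; nothing is said about data after it.
- Section 6.4.3: subjects discontinued before or during EUS are not replaced.
- Section 7.5: "when there are bugs in the software, doctors can still operate under their own judgment".
- Section 8.5: the main analysis uses the PP set (no significant deviation). The FAS is supportive; it keeps shedding cases but drops culling cases, a term that is not defined.

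**The concern.** Randomisation makes the two arms comparable at the start of the examination. A withdrawal ground tied to not using the test device can undo that, because it gives one arm an exit that the other lacks. The person who decides whether EndoAngel is used knows the allocation and can see how the scan is going. If the software is abandoned more often in awkward examinations, those examinations may leave the experimental arm while equally awkward control examinations stay.

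Two things are at stake. The first is the primary comparison of missed structures. The second is information about the device: how often EndoAngel fails or is set aside is part of the answer to whether it helps in practice, and the plan does not ask for it to be reported.

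**Working it through.** **1. Which arm can meet the ground?** Section 6.4.2 does not name EndoAngel. Section 7.4 calls the experiment's instrument software, section 9 describes no other device, and controls have no EndoAngel to set aside. No matching rule covers a control examination in which EndoAngel is used. The natural reading is the experimental arm only.

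**2. How could such a subject leave the comparison?** Not through section 6.4 alone, which keeps earlier data, and not necessarily through the FAS, which keeps shedding cases. The route is section 8.5: a subject withdrawn for device non-use is a likely significant deviation and so is out of the PP main analysis. The same subject might also be classed as culling and be out of the FAS, since culling is undefined. If kept, the record may be truncated, because only data from before discontinuation are promised.

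**3. The plan's sample size.** Inputs from section 8.4: 20% versus 8%, two-sided 5%, power 80%, dropout 10%. With the unpooled-variance formula,

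n per arm = (1.960 + 0.842)² × (0.20×0.80 + 0.08×0.92) / 0.12² = 7.85 × 0.2336 / 0.0144 ≈ 127.3, rounded up to 128.

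Total 256, and 256/0.90 = 284.4, rounded up to 285. The stated figure is reproduced and is not in dispute. It does not address one-arm removal.

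**4. Illustration with no true effect.** Assumptions: a per-patient proportion, as section 8.4 uses; 142 per arm (285/2, rounded down); a true rate of 20% in both arms. A fraction f of the experimental arm is removed, with missed rate m among those removed. The documents give neither f nor m.

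Apparent experimental rate = (0.20 − f·m)/(1 − f). Rejection probability is from a two-sided 5% two-proportion z test, 142 controls against 142(1 − f).

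| f | m | apparent rate | type I error |
|---|---|---|---|
| any | 20% | 20.0% | 5.0% |
| 5% | 40% | 18.9% | 5.5% |
| 5% | 60% | 17.9% | 7.3% |
| 10% | 40% | 17.8% | 7.4% |
| 10% | 60% | 15.6% | 15.7% |
| 15% | 60% | 12.9% | 33% |

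One row in full: f = 10%, m = 60% gives (0.20 − 0.06)/0.90 = 0.1556, a spurious gain of 4.4 points against the planned 12. With 142 and 127.8 subjects the pooled rate is 0.179, the null standard error 0.0467 and the alternative standard error 0.0464. The favourable tail is Φ((0.0444 − 1.96×0.0467)/0.0464) ≈ 0.155 and the other tail about 0.002, together 0.157.

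**5. The opposite direction.** If the same subjects are kept and truncation makes each count as missed, the experimental rate is 0.20 + f(1 − m). At f = 10% this is 26% for m = 40% and 24% for m = 60%: 4 to 6 points against EndoAngel. Section 4.1 counts structures not scanned and does not say how structures never reached in a stopped examination are handled, so neither direction is excluded.

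**The case against.** Much of the opposing case stands. The clause is optional and framed as safety. Section 6.4 keeps earlier data and the FAS keeps shedding cases, so full removal, as modelled above, applies to the PP set and not to every analysis. No document gives a frequency of non-use or a missed rate for such examinations.

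A reader might infer several stronger things that the documents do not support:

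- *That only the experimental arm can ever be affected.* This is the natural reading, not a stated fact. If the specified instrument meant the echoendoscope, either arm could meet the ground.
- *That the bias must favour EndoAngel.* It does so in the PP set only if the removed examinations are worse than average; step 5 gives a case that runs the other way.
- *That structures seen after withdrawal are never recorded, so a switch to the FAS could not help.* No section says recording stops. Section 6.4 is silent on later data, which is a gap and not a prohibition.
- *That sections 7.5 and 6.4.2 contradict each other outright.* Section 7.5 concerns continuity of care. A patient could finish a conventional EUS and still be out of the study. The two are in tension, because section 7.5 implies that the outcome could usually still be observed.
- *That type I error could approach one half.* At f = 10% this requires every removed examination to count as missed, so that half of the arm's expected misses (0.10 of 0.20) fall in the removed tenth. That is an extreme corner.

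What remains is a post-randomisation exit linked to device use, open to an unblinded operator, with a main analysis set likely to exclude those who take it.

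**Conclusion.** The concern holds in this form. On the natural reading, section 6.4.2 creates a withdrawal ground specific to the experimental arm, and sections 6.4 and 8.5 together make it likely that such examinations leave the primary comparison or enter it truncated.

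Its size cannot be derived from the documents. With 10% of the experimental arm removed and 40% to 60% missed among them, PP type I error is about 7% to 16%. It stays at 5% if those removed resemble the rest, and the bias reverses if truncated examinations are kept and their unscanned structures count as missed. These figures rest on assumed fractions and missed rates, and on treating the endpoint as a per-patient proportion.

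Sections 6.4, 6.4.2, 7.5 and 8.5 need to be reconciled. Outcomes that go unrecorded during an examination may not be recoverable later, so this should be settled before or during enrolment and not left to the analysis.

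**What to change.** - **Sections 6.4 and 6.4.2:** state that non-use or failure of EndoAngel is a deviation to be recorded, and that it does not by itself end outcome recording or remove the subject from the analysis. Say what the specified instrument is. The safety withdrawal grounds themselves are for the sponsor to reconcile with section 7.5.
- **Recording:** whenever the EUS continues, record structures, stations, times and lesions to its end. State in section 4.1 how structures not reached in an examination stopped early are counted.
- **Section 8.5:** analyse every randomised subject in the assigned arm as the main analysis, with PP as supportive. Define culling without reference to device use.
- **Reporting:** give the frequency, timing and reasons for non-use.

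The cost is a wording amendment and one CRF field; no extra procedure is needed. The downside is that the estimated effect may be smaller. If the planned 8% describes only examinations in which EndoAngel was used, and abandoned ones have 40% missed, then 2% non-use gives 0.98×8% + 0.02×40% = 8.6% in the whole arm, and power with 142 per arm is 78% instead of 83%. At 10% non-use the rate is 0.90×8% + 0.10×40% = 11.2% and power is 53%. The sponsor should therefore form a view on how common non-use will be.

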4.1. Primary Endpoint

1) Missed scanning rate of adjacent important anatomical structures in pancreatic endoscopic ultrasonography:

It was calculated by dividing the number of important anatomy that is not scanned in the actual EUS pancreas by the number of EUS.

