4.2. Secondary Endpoints

- 1) Pancreatic lesions detection rate: It was calculated by dividing the total number of patients being detected pancreatic lesions by the number of EUS.
- 2) Cholangiopancreatic duct lesions detection rate: It was calculated by dividing the total number of patients being detected cholangiopancreatic duct lesions by the number of EUS.
- 3) The average number of scanning in the pancreatic standard station of endoscopic ultrasonography: It was calculated by dividing the total number of scanning in the pancreatic standard station by the number of EUS.
- 4) Detection rate of lesions in different pancreatic standard stations of endoscopic ultrasonography: It was calculated by dividing the number of patients with pancreatic lesions and Cholangiopancreatic duct lesions in the different standard stations by the number of EUS.
- 5) Missed scanning rate of adjacent vital anatomical structures in different pancreatic standard stations of endoscopic ultrasonography: It was calculated by dividing the number of important anatomy that is not scanned in the different standard stations by the number of EUS.
- 6) Mean scanning time in different pancreatic standard stations of endoscopic ultrasonography: It was calculated by dividing the total scanning time by the number of EUS.

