6.4.3 Replacement

Subject will be deemed to have commenced the study upon completion of the informed consent process, and any subject who has been discontinued prior to or during the EUS examination will not subsequently be replaced by other subjects.

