8.5. Statistical analysis set

All patients who met the inclusion and exclusion criteria were considered eligible for recruitment.

The two analysis sets in this study are defined as follows:

- The full analysis set (FAS) population analysis set will contain all eligible cases and shedding cases, but does not include culling cases.
- The Compliance (PP) population analysis set will include all subjects in the FAS analysis set with no significant deviation from the program.

Intention-to-treat and conformity analysis sets should be used to analyze the primary efficacy endpoints. The main analysis will be based on the PP analysis set. FAS analysis was regarded as supportive analysis.

9. Device Description

EndoAngel

Version: EA 2301

10. Abbreviations

Abbreviations	Full Name	Chinese
AE	Adverse Event	不良事件
CFDA	China Food and Drug Administration	国家食品药品监督管理总局
CNDA	China National Drug Administration	国家食品药品监督管理总局
CRF	Clinical Record File	病例报告表
CTCAE	Common Terminology Criteria for Adverse Events	不良事件常规评价标准
EC	Ethical Committee	伦理委员会
ICD	Informed Consent Document	知情同意文件
ICF	Informed Consent Form	知情同意书

ITT	Intention to Treat	意向治疗分析集
PP	Per Protocol	符合方案集
SAE	Serious Adverse Event	严重不良事件
EUS	Endoscopic ultrasonography	超声内镜
EUS-FNA	Endoscopic Ultrasound Guided Fine Needle Aspiration	超声内镜引导下细针穿刺活检

11. References

- [4] *Cancer incidence and mortality statistics worldwide and by region*. Available: <https://gco.iarc.fr/today/data/factsheets/cancers/13-Pancreas-fact-sheet.pdf>

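### A started EUS that cannot be completed triggers withdrawal, and sections 6.4 and 8.5 let such examinations leave the main analysis or enter it truncated, for a reason linked to the primary endpoint

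*Combined protocol and SAP*

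**What the plan says.** - **Trigger.** Section 6.4.2 instructs: "If the following serious cases occur, please withdraw during the operation". The list is perforation, bleeding, allergy to narcotic drugs and, as item 4, "Unable to complete EUS due to obstruction or other reasons". The last two words of item 4 are not limited further.
- **Primary endpoint.** Section 4.1 computes the missed scanning rate by "dividing the number of important anatomy that is not scanned in the actual EUS pancreas by the number of EUS".
- **Status and data after withdrawal.** Section 6.4: "If serious program deviation, withdrawal, or death occurs, the subject study is considered to be suspended". For a subject who discontinues after consent, "the data before the discontinuation will still be included in the study-related analysis".
- **Replacement.** Section 6.4.3: "any subject who has been discontinued prior to or during the EUS examination will not subsequently be replaced by other subjects".
- **Analysis sets.** Section 8.5 says the FAS "will contain all eligible cases and shedding cases, but does not include culling cases". The PP set is the FAS without significant deviations, and PP is the main analysis with FAS supportive. Neither culling nor significant deviation is defined.
- **Blinding.** Section 6.5.2 lists subjects and evaluators as blinded, not the operator. The synopsis has the operating physician work with or without the AI prompt.
- **Scanning time.** Section 4.2, item 6: "It was calculated by dividing the total scanning time by the number of EUS".

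**The concern.** Items 1 to 3 of the list are medical events. Item 4 is different in kind: it describes whether the scan was completed, and an examination stopped early leaves structures unscanned, which is what the primary endpoint counts. The operator, whose experience of the examination decides whether it can be completed, sees the allocation. A prompt about scanning could plausibly change how long an operator persists.

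The plan then does not fix what happens to such an examination. It may stay in with the unreached structures counted as missed, stay in with those structures unrecorded, or be left out of the PP set (or of both sets, if it is culled). The choice could be made after the result is known. If the arms differ in how many examinations are stopped, or in how these are classified, the primary comparison moves for a reason other than scanning quality. The secondary endpoints are exposed as well: a truncated examination counts as one EUS in the denominator but contributes a shorter scanning time and less opportunity to detect lesions.

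**Working it through.** **1. The plan's own figure.** Inputs from section 8.4: 20% control, 8% experimental, two-sided 5%, 80% power, 10% dropout. Section 6.5.1 gives 1:1 allocation. With unpooled variance:

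n per arm = (1.960 + 0.842)² × (0.20×0.80 + 0.08×0.92) / 0.12² = 7.849 × 0.2336 / 0.0144 = 127.3, rounded up to 128. Total 256, and 256 / 0.90 = 284.4, rounded up to 285.

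The sample size is reproduced and is not in dispute.

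**2. Route of an item 4 examination through the text.**
- Section 6.4.2 withdraws the subject. By itself this removes no data.
- Section 6.4 retains what was recorded before the stop, but does not say whether unreached structures count as not scanned.
- Section 8.5 retains dropouts in the FAS unless they are culled (undefined).
- Section 8.5 takes the main result from PP, which excludes significant deviations (undefined). Section 6.4 names withdrawal beside serious deviation as a ground for suspending the subject.

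Exclusion from the main analysis is thus permitted but not certain. Truncation is permitted wherever the examination is kept.

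**3. Upper illustration: loss in one arm only.** Assumptions: one binary miss per examination (as section 8.4 implies, although section 4.1 defines a count per EUS), 128 per arm, true rate 20%, every affected examination has a miss. The numbers affected (6 and 13, about 5% and 10% of an arm) are assumptions, as the documents give no rate of incomplete examinations. Expected misses: 0.20 × 128 = 25.6.

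| Affected | Dropped | Kept but scored as no miss |
|---|---|---|
| 6 | (25.6 − 6)/(128 − 6) = 16.1% | 19.6/128 = 15.3% |
| 13 | (25.6 − 13)/(128 − 13) = 11.0% | 12.6/128 = 9.8% |

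The last column applies if the unreached structures go unrecorded and no miss was noted before the stop. Dropping 13 means that about half (13/25.6) of that arm's misses were incomplete procedures.

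**4. False-positive risk in the same one-arm case.** No true effect, 20% in both arms, 142.5 per arm (285/2), and a fraction f of the missed examinations removed from one arm. The observed rate there is 0.20(1 − f)/(1 − 0.20f). Two-sided pooled z test:
- f = 10% (2% of the arm): 18.4%, false difference 1.6 points, type I error 6.4%
- f = 25% (5% of the arm): 15.8%, 4.2 points, 14.9%
- f = 50% (10% of the arm): 11.1%, 8.9 points, 51.7%

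**5. Same f in both arms.** True rates 20% and 8%, observed rate p(1 − f)/(1 − pf), 142.5 per arm before removal, pooled formula:

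| f | Control | Experimental | Difference (points) | Power |
|---|---|---|---|---|
| 0 | 20.0% | 8.0% | 12.0 | 83.5% |
| 10% | 18.4% | 7.3% | 11.1 | 79.9% |
| 25% | 15.8% | 6.1% | 9.7 | 73.2% |
| 50% | 11.1% | 4.2% | 6.9 | 57.2% |

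**The case against.** The strongest reply is that the plan already retains these subjects. Section 6.4 includes the data before discontinuation, section 8.5 keeps dropouts in the FAS, and section 6.4.3 bars replacement. A reader might infer from item 4 that withdrawal deletes the examination; the documents do not say so. This stands. What it leaves open is the scoring of unreached structures and membership of the PP set, and PP gives the main result.

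Second, section 6.4.2 opens with safety and calls its list serious cases. Read that way, the open wording means other serious impediments, not a missed landmark, and an operator who overlooks a structure still completes the EUS and is counted. It would also be too strong to say that an incomplete examination is the endpoint event: the endpoint counts unscanned structures, which an incomplete examination produces in varying number. Both points are fair. Obstruction is largely a patient factor, so the concern rests mainly on the unlimited remainder of item 4, which nothing in the text confines to safety.

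Third, the sizes above are worst cases. A reader might take the 10% dropout allowance in section 8.4 as the expected number of item 4 cases. It is not tied to any cause, and consent withdrawal and pre-procedure withdrawal draw on it too. A late stop would also carry fewer misses than an early one.

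Fourth, counting every unreached structure as not scanned charges obstruction or a complication to scanning quality, while exclusion criteria 6 and 7 in section 3.2 suggest interest in patients whose anatomy can be observed. That is a reasonable argument about what to estimate. It is met by a prespecified sensitivity analysis, not by leaving the rule open.

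**Conclusion.** The concern holds in a limited form. Item 4 of section 6.4.2, the undefined terms in section 8.5 and the missing scoring rule together allow incomplete examinations to be dropped from the main result, or to enter it truncated, for a reason linked to the primary outcome and with an operator who knows the arm.

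The frequency is unknown. So is the direction: a reader might infer that the rule favours EndoAngel, but the documents do not show in which arm more examinations would be stopped. One-arm loss of 6 or 13 of 128 examinations, all with a miss, moves 20% to about 16% or 11%, which is 3.9 or 9.0 of the planned 12 points. These are upper illustrations under a binary endpoint. Equal proportional loss in both arms mainly costs power: from 83.5% to 79.9% if a tenth of missed examinations go. The figure of 285 is unaffected.

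**What to change.** Leave the clinical decision to stop a procedure as it is, and separate it from membership of the analysis.

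1. In sections 6.4.2 and 8.5, state that stopping an EUS is not withdrawal from the analysis, and that incompleteness is neither a reason for culling nor a significant deviation. Changing 6.4.2 alone would not be enough, because exclusion runs through 8.5.
2. Keep every randomised subject whose EUS was started in the assigned arm's primary analysis, with structures not reached counted as not scanned. Fix this before any results by arm are seen.
3. Record the reason for stopping and the last station reached, and report incomplete examinations by arm.
4. Add one sensitivity analysis that excludes examinations stopped for mechanical obstruction or a complication.
5. Report scanning time with incomplete examinations shown separately by arm. A mean restricted to subjects who reached the station conditions on something that happened after randomisation, so it should be supplementary only.

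Cost: wording in two sections, two CRF fields, and a few lines of tables. No extra subjects are needed. The downside is slightly higher miss rates in both arms, some of them due to patient factors, which the sensitivity analysis addresses.
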